1.3. Schedule of Activities (SoA)

Phase	Screening	Treatment									Follow-up ^e	Notes	
		Cycle 1			Cycle 2		Cycle 3	Cycles 4-6	Cycle 7 until EOT	EOT			
CYCLE (defined as 28 days)	Within 28 days before CID1, unless otherwise specified												
CYCLE DAY		Day 1	Day 8 (±1 day)	Day 15 (±1 day)	Day 1	Day 15	Day 1	Day 1	Day 1	Day 1	Within 30 days after last dose	Every 6 months (±14-day)	Unless otherwise specified, study visits/procedures have a ±2-day time window
Screening													
Informed consent (ICF) ^a	X												Must sign the ICF before first study-related activity.
Medical history and demographics, including any prestudy therapy for SGC	X												
Inclusion/exclusion criteria	X	X											
Urine or serum β-hCG pregnancy test	X 7 days	As clinically indicated, by urine or serum test											Women of childbearing potential only. Screening test within 7 days of first dose.
Study Intervention Administration													
Dispense apalutamide		X			X		X	X	X				Apalutamide and GnRH agonist will be administered according to Section 6.1, Study
Dispense and administer GnRH agonist		X			X		X	X	X				

Phase	Screening	Treatment									Follow-up ^c	Notes
		Cycle 1			Cycle 2		Cycle 3	Cycles 4-6	Cycle 7 until EOT	EOT		
CYCLE (defined as 28 days)	Within 28 days before C1D1, unless otherwise specified	Cycle 1			Cycle 2		Cycle 3	Cycles 4-6	Cycle 7 until EOT	EOT	Follow-up	
CYCLE DAY		Day 1	Day 8 (±1 day)	Day 15 (±1 day)	Day 1	Day 15	Day 1	Day 1	Day 1	Within 30 days after last dose	Every 6 months (±14-day)	Unless otherwise specified, study visits/procedures have a ±2-day time window
												Interventions Administered.
Dose compliance					X		X	X	X	X		Includes a tablet count (refer to Section 6.4).
Efficacy Evaluations^b												
CT or MRI (neck, chest, abdomen, and pelvis)	X						X	X	X		(X) ^c	Screening, Cycles 3, 5, 7, 9, 11 then q3 cycles beginning at Cycle 13. The same modality (CT or MRI) should be used throughout the study. Imaging visits may occur up to 7 days before cycles requiring images. Unscheduled assessments may be performed if signs of disease

Phase	Screening	Treatment									Follow-up ^e	Notes
		Cycle 1			Cycle 2		Cycle 3	Cycles 4-6	Cycle 7 until EOT	EOT		
CYCLE (defined as 28 days)	Within 28 days before C1D1, unless otherwise specified	Cycle 1			Cycle 2		Cycle 3	Cycles 4-6	Cycle 7 until EOT	EOT	Follow-up	

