Keys: AR=androgen receptor; β-hCG=beta human chorionic gonadotropin; C1D1=Cycle 1 Day 1; CT=computed tomography; CTC=circulating tumor cell; E2=estradiol; ctDNA/RNA=circulating tumor DNA/RNA; ECG=electrocardiogram; ECOG-PS=Eastern Cooperative Oncology Group performance status; eCRF=electronic case report form; EOT=end-of-treatment; FDG-PET=fluorodeoxyglucose-positron emission tomography; FFPE=formalin-fixed paraffin-embedded; FSH=follicle stimulating hormone; GnRH=gonadotropin-releasing hormone; HER2=human epidermal growth factor receptor 2; HDL=high-density lipoprotein; ICF=informed consent form; LDL=low-density lipoprotein; LH=luteinizing hormone; MRI=magnetic resonance imaging; PK=pharmacokinetic(s); PSA=prostate-specific antigen; q3 cycles=every 3 cycles; ULN=upper limit of normal; T3=triiodothyronine; T4=free thyroxine; TSH=thyroid-stimulating hormone.

Footnotes:

- a. Must sign the ICF before first study-related activity.

- b. Every effort should be made to document radiographic progression, even after discontinuation of treatment for safety or tolerability reasons (eg, AE) but prior to subsequent therapy.
- c. If a participant discontinues study intervention for safety or tolerability reasons (eg, AE), radiographic evaluations must be continued until disease progression but prior to subsequent therapy according to the same schedule as the one of prediscontinuation (every 2 cycles or every 3 cycles beginning at Cycle 13 from Cycle 1 Day 1) unless (s)he withdraws consent for follow-up.
- d. Locally performed. For fasting laboratory assessments, if the participant has not fasted before the visit, the visit may proceed, but the participant must return within 72 hours in a fasted state to provide the necessary sample(s) for the assessments.
- e. Follow-up for survival will continue until death, withdrawal of consent, lost to follow-up or until the end of the study. Deaths regardless of causality will be reported in the eCRF. Serious adverse events that occur after 30 days following the last drug administration thought to be related to study intervention will be collected and reported via the Serious Adverse Event form within 24 hours of discovery or notification of the event and documented (refer to Section 8.3.1).
- f. Fasting state is defined as 8 hours without food or drink, with the exception of water.
- g. A blood sample will be collected at any time between 0.5 to 4 hours after the apalutamide administration.

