4. STUDY DESIGN

4.1. Overall Design

This is an open-label, single-arm, multicenter, Phase 2 study to evaluate the efficacy and safety of apalutamide in combination with a GnRH agonist in participants with AR expressing locally advanced or recurrent/metastatic SGC.

A target of 24 participants will be included in this study and receive apalutamide and a GnRH agonist.

The study will consist of a screening phase, a treatment phase, and a follow-up phase. The study is anticipated to end approximately 42 months after the first participant is consented.

The study will be conducted in an outpatient setting and a treatment cycle is defined as 28 days. Study intervention will continue until disease progression, unacceptable toxicity, death, or the end of the study. Study intervention will be discontinued if a participant meets any of criteria described in Section 7.1, Discontinuation of Study Intervention.

After discontinuing study intervention, participants will be contacted every 6 months (refer to the SoA in Section 1.3) until death or the end of the study.

Participants will be monitored for safety starting from the signing of informed consent until 30 days after the last dose of study intervention. Adverse events including laboratory AEs will be graded and summarized using version 5.0 of the National Cancer Institute-Common Terminology Criteria for AEs (NCI-CTCAE). Dose modifications will be made as required according to dose modification rules (Section 6.6). An independent central radiology review will be used to reduce potential bias during data collection and evaluation of the primary endpoint of ORR and secondary endpoints including PFS (Section 9).

A diagram of the study design is provided in Section 1.2, Schema.

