4.3. End of Study Definition

End of Study Definition

The end of study is considered as the last scheduled study assessment shown in the SoA (Section 1.3) for the last participant in the study, the decision of termination by the sponsor or regulatory authorization. Enrolled participants will be transitioned from study intervention to commercial product once commercial product is available by a doctor's prescription.

Study Completion Definition

A participant will be considered to have completed the study if he or she has died before the end of the study, has been lost to follow-up, or withdrawn consent before the end of the study.

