7. DISCONTINUATION OF STUDY INTERVENTION AND PARTICIPANT DISCONTINUATION/WITHDRAWAL

7.1. Discontinuation of Study Intervention

For all participants in the study, discontinuation from study intervention will not result in automatic withdrawal from the study. A participant's study intervention must be discontinued if:

- The participant withdraws consent to receive study intervention
- The investigator believes that for safety reasons or tolerability reasons (eg, AE) it is in the best interest of the participant to discontinue study intervention
- The participant becomes pregnant Refer to Section 10.5, Appendix 5, Contraceptive Guidance and Collection of Pregnancy Information
- Noncompliance with continued treatment or procedure requirements that the sponsor considers would impact the study evaluation despite frequent corrective instruction
- Documented radiographic (RECIST version 1.1) disease progression
- More than 2 dose level reductions for treatment-related AEs (Table 1 and Table 2)
- Seizure of any grade or Grade 4 neurotoxicity
- The participant receives concurrent (non-protocol) anticancer treatment

If a participant discontinues study intervention for any reason but does not withdraw consent for follow-up, then the scheduled assessments must be continued according to the follow-up phase in the SoA (Section 1.3). The EOT visit should be conducted within 30 days after the last dose of study intervention. The reason(s) a participant discontinues study intervention will be recorded on the eCRF. Once a participant discontinues treatment with the study intervention, the participant will not be permitted to be retreated.

In instances where the investigator feels a participant may continue to receive clinical benefit from further treatment with study intervention after documented disease progression, the case should be discussed with the sponsor's medical monitor, who in conjunction with the investigator, will determine if treatment beyond RECIST version 1.1 defined progression is indicated. If the participant is treated beyond documented disease progression, disease assessments will continue according to the schedule in Section 1.3 and the investigator and sponsor medical monitor will review clinical benefit after each disease assessment.

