### **3.1. Selection rule of response evaluable participants who are used in IA and FA**

In the primary analysis of interim and final analysis, 12 and 24 response evaluable participants (response evaluable population) who has been evaluated at least 24 weeks from the initiation of study intervention or whose disease evaluation of primary endpoint has been determined within 24 weeks after the initiation of study intervention are analyzed respectively. ie, The 12 and 24 response evaluable participants who meet the at least one condition listed below will be analyzed in the primary analysis of IA and FA respectively.

1. Who evaluated at least 24 weeks from the initiation of study intervention (has cycle 7 visit efficacy disease assessment).
2. Whose ICRR disease evaluation is confirmed as  $\geq$ PR within 24 weeks from the initiation of study intervention (disease evaluation of primary endpoint is determined at the first confirmed date of  $\geq$ PR)
3. Whose ICRR disease evaluation is PD within 24 weeks from the initiation of study intervention (disease evaluation of primary endpoint is determined at the first PD date of ICRR)
4. Who completed study participation (disease evaluation of primary endpoint is determined at death date, the date of withdrawal from consent, the last contact date if the participant is lost of follow up)
5. Who started subsequent therapy (disease evaluation of primary endpoint is determined at the date of subsequent therapy initiation)

If there are more than 12 or 24 response evaluable participants who meet the condition above at the timing of IA or FA, response evaluable participants are selected in order of the date of obtaining informed consent, the date of first study intervention and study site number from the participants who meet the condition above.

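### SAP 3.1 conflicts with SAP 1.2 and can leave a non-responder with no route into the decision set by the cutoff; if a surplus participant qualifies, this gap on its own can only raise the primary ORR

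*SAP*

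**What the plan says.** SAP 3.1 restricts the primary analysis sets to response-evaluable participants who satisfy at least one of five conditions:

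1. "Who evaluated at least 24 weeks from the initiation of study intervention (has cycle 7 visit efficacy disease assessment";
2. ICRR-confirmed PR or better within 24 weeks;
3. "Whose ICRR disease evaluation is PD within 24 weeks from the initiation of study intervention";
4. completed participation, through death, withdrawal of consent or loss to follow-up;
5. start of subsequent therapy.

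If more qualify than are needed, they are taken in order of consent date, then "the date of first study intervention and study site number from the participants who meet the condition above". SAP 3 says that efficacy and futility rest on this fixed set alone.

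SAP 1.2 describes the same two triggers as 24 weeks of observation and mentions no scan. The main text of SAP 3 and Protocol 9.5 speaks of 24 weeks of evaluation, or of an endpoint already determined.

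Four protocol rules bear on who can meet the conditions:

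- Section 7.1 stops treatment for documented RECIST progression, without requiring that ICRR agree, and for noncompliance. It adds that "discontinuation from study intervention will not result in automatic withdrawal from the study".
- SoA footnote c (Section 1.3) says: "If a participant discontinues study intervention for safety or tolerability reasons (eg, AE), radiographic evaluations must be continued until disease progression".
- Section 4.3 says: "A participant will be considered to have completed the study if he or she has died before the end of the study"; loss to follow-up and withdrawal of consent count in the same way.
- Section 4.1 says: "After discontinuing study intervention, participants will be contacted every 6 months".

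**The concern.** The list in SAP 3.1 is closed, and no condition on it is met by elapsed time alone. A participant can be response evaluable (SAP 2.2 asks for one postbaseline assessment) and still meet none of the five by the cutoff. There are two main examples: treatment stopped before week 24 for investigator-read progression that ICRR does not confirm, and treatment stopped before week 24 for noncompliance.

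Such a participant has no confirmed response, and has no scan at or after Cycle 7 on which one could be established. The gap therefore holds only non-responders, and selection in consent order among qualifiers passes their places to later participants. SAP 3 foresees a surplus: enrolment continues through the interim, and the text provides for 25 or more at the final. At stake are the observed ORR, the interim futility decision and the margin below the 2.5% type I error limit.

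**Working it through.** **1. The plan's own figures.** Inputs: null ORR 14%, alternative 40% (SAP 1.4); stop for futility at 1 or fewer of 12; declare efficacy at 7 or more of 12, or 8 or more of 24 (SAP Table 1). The chance of declaring efficacy is P(X12 ≥ 7) + Σ(x = 2 to 6) P(X12 = x) · P(Y12 ≥ 8 − x).

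- At 14%: 0.00044 + 0.01287 = 0.0133.
- At 40%: 0.1582 + 0.6472 = 0.8054.

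These match the 1.3% and 80.5% in Protocol 9.5.

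**2. The example case against the five conditions.** Take a non-responder who stopped before week 24 for investigator-read PD, not PD by ICRR.

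- Condition 1: Cycle 7 Day 1 falls 6 × 28 = 168 days (24.0 weeks) after first dose. Footnote c does not require scans after this type of stop, so there may be none. Not met if the parenthesis governs.
- Condition 2: no confirmed response. Not met.
- Condition 3: no ICRR PD. Not met.
- Condition 4: stopping treatment is not study completion (Protocol 4.3, 7.1). Not met.
- Condition 5: no new therapy. Not met.

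Conditions 4 and 5 have no time limit, so the participant may qualify later. With contact every 6 months, this may become known late.

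A missed Cycle 7 scan followed by a Cycle 9 scan (8 × 28 = 224 days, week 32) is a separate ambiguity. It satisfies the main wording of condition 1 but not the parenthesis.

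**3. Size.** The documents give no frequency. Assume k gap non-responders are passed over for every 24 analysed. The gap share is q = k/(24 + k), and the ORR among qualifiers at the null is 0.14/(1 − q) = 0.14 × (24 + k)/24. For k = 1, 2, 3 this is 0.1458, 0.1517, 0.1575.

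The table gives the chance of declaring efficacy at a true ORR of 14% under three assumptions, and the chance of the interim futility stop.

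| k | ORR among qualifiers | Gap at interim only | Half resolved by final | Unresolved at both | Futility stop |
|---|---|---|---|---|---|
| 0 | 14.0% | 1.33% | 1.33% | 1.33% | 48.3% |
| 1 | 14.6% | 1.34% | 1.50% | 1.68% | 46.0% |
| 2 | 15.2% | 1.34% | 1.67% | 2.10% | 43.7% |
| 3 | 15.8% | 1.35% | 1.86% | 2.59% | 41.5% |

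The interim-only column takes the first 12 non-gap participants at the interim and the first 24 in consent order at the final, with gap participants counted as non-responders. The half-resolved column is simulated (1 million trials per k, standard error about 0.014 percentage points). The other columns are exact.

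With the gap unresolved at both analyses, 2.5% is reached at q = 0.1054, that is k = 24 × 0.1054/0.8946 = 2.83. Three passed over and 24 analysed need 24 + 3 = 27 response-evaluable participants.

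**4. What the table leaves out.** A participant with ICRR PD can qualify at the first scan, at Cycle 3. A responder needs a further scan at least 4 weeks after the first. Among early qualifiers this timing favours non-responders and pulls the interim ORR down. The two effects can roughly cancel. Assume one participant enrolled per month, PD at week 8 in 30% and at week 16 in 20% of non-responders, and half of responses confirmed at week 16 with the rest at week 24. With q = 4% (k = 1), the simulated interim ORR is about 14.1% against a true 14%. With less early PD the offset largely disappears.

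**The case against.** The strongest objection is that there may be no gap. SAP 1.2 speaks of observation for 24 weeks; on an elapsed-time reading the participant enters as a non-responder and nothing is lost. This stands as a possible reading. But SAP 3.1 is the more specific text, SAP 3 refers to it for the detail of selection, and its parenthesis names the Cycle 7 assessment. The two sections need to be reconciled; exclusion is not proven.

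Second, the gap is narrow. Scans continue after safety or tolerability stops, treatment and scans may continue beyond progression, and an unreachable participant is treated as withdrawn (Protocol 7.2.2) and enters by condition 4. Protocol 7.1 also continues scheduled assessments after a stop for any reason. All of this stands, except that the last point refers to the follow-up phase of the SoA, where the imaging entry is bracketed and tied to footnote c.

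Third, displacement at the final needs enrolment above the target of 24 (Protocol 4.1). Without it the final analysis waits and nobody is replaced. This stands.

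A reader might infer that the primary ORR is biased upward overall, or that the 2.5% limit is breached. The documents support neither: the opposite timing effect leaves the net direction at the interim open, and a breach needs about three unresolved cases at both analyses plus over-enrolment. A reader might also add non-responders to 8 of 24 and note that the 95% lower limit at 8 of 27 is 13.8%, below 14%. That describes the supplemental all-data analysis in SAP 5.2; the change proposed here keeps 24.

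**Conclusion.** The concern holds as a conflict between SAP 3.1 and SAP 1.2 with a small, conditional effect. It should be fixed. If the parenthesis governs, an identifiable kind of non-responder can be passed over in the set that decides efficacy and futility. That mechanism alone can move the primary ORR only upward.

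The effect is zero if nobody is in the gap. An interim-only gap changes type I error by at most 0.02 percentage points for k up to 3. A gap of one or two unresolved at both analyses uses part of the margin (1.68%, 2.10%) but stays within 2.5%. All these figures rest on the assumed k and on a surplus participant being available. The supplemental all-data ORR would show the difference but does not drive the decision.

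**What to change.** Amend SAP 3.1, with matching wording in Protocol 9.5 and SAP 1.2:

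- **Condition 1** is met by any ICRR-read disease assessment at or after the Cycle 7 imaging time point. This includes the early window in the SoA, which says "Imaging visits may occur up to 7 days before cycles requiring images" (168 − 7 = 161 days, week 23).
- **New condition 6:** a response-evaluable participant who meets none of conditions 1 to 5 once the Cycle 7 imaging window has closed keeps the consent-order place and counts as a non-responder, unless ICRR-confirmed CR or PR is documented by the data cutoff. The only deferral is for an unconfirmed ICRR CR or PR awaiting its confirmatory scan, and it ends when the next scheduled imaging window (Cycle 9) closes.

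The end point for the deferral matters. A general exception for pending scans would never close for a participant who stays on schedule but keeps missing them.

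The cost is two lines in the SAP plus the matching text. No new data are needed, and no treatment or scan schedule changes. The observed ORR may be slightly lower. If 14% and 40% are the rates among all response-evaluable participants, gap cases included, type I error and power for this mechanism return to 1.33% and 80.5%. If 40% was meant only for those who qualify, a 4% gap gives 0.40 × 0.96 = 38.4% and power of 75.9%.

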The final analysis will be performed when 24 response evaluable participants (response evaluable population) who has been evaluated at least 24 weeks from the initiation of study intervention are observed. The final analysis is performed based on the data from 24 response evaluable participants (response evaluable population) who has been evaluated at least 24 weeks from the initiation of study intervention or whose disease evaluation of primary endpoint has been determined within 24 weeks after the initiation of study intervention. If 25 or more response evaluable participants who meet the condition above are available at the timing of final analysis, only the data of 24 response evaluable participants who are selected by the date of obtaining informed consent will be used for primary analysis at the final analysis. The analysis of primary endpoint using data including 25th or more response-evaluable participants (order of the date of obtaining informed consent) and thereafter will be used for supplemental analysis.

As mentioned above, the fixed number (12 and 24) of response evaluable participants who meet the condition above are used in the analysis of primary endpoint at the interim and the final analysis for efficacy and futility determination. The additional supplemental analyses may be conducted when the study ends ([Section 4.3](#)), upon a request from regulatory authorities or based on a sponsor's decision.

The actual Type-1 error and power are 1.3% and 80.5% if the interim analysis is conducted when the 12 response-evaluable participants are observed at least 24 weeks after the initiation of study intervention.

The sponsor will establish a data cutoff date for interim and final analyses. The sponsor will determine whether futility or efficacy will be declared based solely on the result of primary endpoint which based on the independent central radiology review and the efficacy and futility boundaries of [Table 3](#).

Table 3: Efficacy and Futility Boundaries Using Alpha Spending Function

The timing of analysis (Number of Response- evaluable Participants)	Maximum Number of Responders for Futility	Minimum Number of Responders for Efficacy	Cumulative Alpha Spent Based on Alpha Spending Function
12	1	7	0.15%
24	-	8	2.5%

The right most column in [Table 3](#) shows cumulative alpha based on alpha spending function in this study. The Statistical Analysis Plan will describe the planned interim and final analyses in greater detail.

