## 1.4. Sample Size Justification

In this study, ORR of 40% is assumed (Fushimi 2018). Under the alternative hypothesis for ORR of 40%, using an O'Brien-Fleming boundary based on Lan-DeMets' alpha spending function (Jennison 1999), to achieve at least 80% power for rejecting the null hypothesis for ORR of 14% by exact test based on the binomial distribution while maintaining overall 1-sided Type-1 error below 2.5%, at least 24 evaluable participants will be required. The null hypothesis of ORR of 14% for the threshold value is an estimate based on published data (Viscuse 2019).

An ORR will be tested using exact test based on the binomial distribution, and the null hypothesis for ORR of 14% will be rejected and efficacy will be declared if statistical significance is observed using an O'Brien-Fleming boundary based on Lan-DeMets' alpha spending function as described in Section 3. Futility analysis is also used in this study. Details are described in Section 3. With 24 evaluable participants and 1 interim analysis based on the boundaries, overall Type-1 error will be lower than the one-sided significance level of 2.5% and power will be higher than 80%. The lower limit of 2-sided 95% Clopper-Pearson confidence interval (CI) for ORR will exceed the threshold value of 14% if efficacy is declared based on the boundaries in Table 1.

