## 3. INTERIM AND FINAL ANALYSIS

An interim analysis will be conducted. To control overall Type 1 error, O'Brien-Fleming boundary based on Lan-DeMets' alpha spending function will be used for analysis of primary endpoint based on the independent central radiology review (ICRR), and the null hypothesis for ORR of 14% will be rejected and efficacy will be declared if statistical significance is observed based on the O'Brien-Fleming boundary of Lan-DeMets' alpha spending function. In the interim analysis, futility analysis is also planned, the study will be concluded futile and will be stopped, if the count of responder is 1 or none. The stopping boundaries for efficacy and futility based on the O'Brien-Fleming boundary of Lan-DeMets' alpha spending function are displayed in [Table 1](#). Enrollment will not pause during interim analysis.

In this study, an interim analysis will be performed when 12 response evaluable participants (response evaluable population) who has been evaluated at least 24 weeks from the initiation of study intervention are observed. The interim analysis is performed based on the data from 12 response evaluable participants (response evaluable population) who has been evaluated at least 24 weeks from the initiation of study intervention or whose disease evaluation of primary endpoint has been determined within 24 weeks after the initiation of study intervention. If 13 or more response evaluable participants who meet the condition above are available at the timing of interim analysis, only the data of 12 response evaluable participants who are selected by date of obtaining informed consent will be used for primary analysis at the interim analysis. (If there are multiple response evaluable participants whose date of obtaining informed consent is the same, who are with earlier date of the first study intervention will be used. If informed consent date and first study intervention date are used and response evaluable participant is still not unique, who are with smaller number of study site number will be used. ie, Response evaluable participants are selected in order of the date of obtaining informed consent, the date of first study intervention and study site number from the participants who meet the condition above.) The analysis of primary endpoint using data including 13th or more response evaluable participants (in the same order of above) and thereafter will be used for supplemental analysis.

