## 5.1. Analysis Specifications

### 5.1.1. Level of Significance

The primary endpoint is tested with 1-sided 2.5% level of significance. The testing of the primary endpoint will be performed according to the O'Brien-Fleming boundary based on Lan-DeMets' alpha spending function with a planned Type 1 error of 2.5% (1-sided). The overall Type-1 error is 1-sided 2.5% for analysis of primary endpoint. The futility and efficacy are declared based solely on the independent central radiology review (ICRR) of primary endpoint and [Table 1](#) of [Section 3](#) whose efficacy boundary is calculated based on the O'Brien-Fleming boundary based on Lan-DeMets' alpha spending function. For easy understanding, the two-sided 95% confidence level is used for calculating confidence interval, unless otherwise specified.

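### The 12 and 24 analysed participants are taken from those already decided, and the trigger wording leaves open whether early deciders count; if they do, the interim set is selected on outcome speed

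*SAP*

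**What the plan says.** SAP 3.1 lists five conditions, any one of which makes a response-evaluable participant available for the primary analysis:

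1. the Cycle 7 disease assessment has been done;
2. the central review has confirmed PR or better within 24 weeks;
3. the central review has found PD within 24 weeks;
4. study participation has ended (death, withdrawal of consent, loss to follow-up);
5. subsequent therapy has started.

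If more than 12 or 24 qualify, the analysed ones should be "selected in order of the date of obtaining informed consent, the date of first study intervention and study site number from the participants who meet" one of these conditions. Consent date therefore orders only those who are already decided.

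The timing is worded differently. SAP 3 says "an interim analysis will be performed when 12 response evaluable participants (response evaluable population) who has been evaluated at least 24 weeks" from first dosing. Protocol 9.5 says "The final analysis will be performed when 24 response evaluable participants" have likewise been evaluated for at least 24 weeks. SAP 1.2 uses observed instead of evaluated. The alternative of an outcome determined before week 24 appears only in the next sentence of protocol 9.5 and SAP 3, which describes whose data are analysed, and in SAP 3.1. No sentence says whether such participants count toward the trigger.

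Enrolment continues through the interim, and efficacy and futility rest solely on the fixed 12 and 24. At the interim "the study will be concluded futile and will be stopped, if the count of responder is 1 or none".

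**The concern.** The exact binomial boundaries assume that membership of the 12 or 24 is unrelated to outcome. Under SAP 3.1, a participant in ongoing stable disease before Cycle 7 is outside the pool. A participant who consented later but already has progression or a confirmed response is inside it and takes the place.

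The interim is where this matters most, because later participants are then certain to exist and a count of 0 or 1 ends the study. A set enriched for fast progression raises the chance of stopping an active treatment. A set enriched for fast response lowers the chance of stopping an inactive one. At the final analysis the same mechanism acts only if there are more than 24 evaluable participants to choose from.

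**Working it through.** **Step 1: the plan's own figures.** Inputs from SAP 1.4, SAP 5.1.1 and SAP Table 1:

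- null: "rejecting the null hypothesis for ORR of 14% by exact test based on the binomial distribution";
- alternative: "In this study, ORR of 40% is assumed";
- level: "The primary endpoint is tested with 1-sided 2.5% level of significance";
- size: "at least 24 evaluable participants will be required";
- boundaries: futility at 1 or fewer of 12, efficacy at 7 or more of 12 or 8 or more of 24.

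With X1 and X2 independent Bin(12, p):

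P(declare) = P(X1 ≥ 7) + Σ(x = 2 to 6) P(X1 = x) · P(X2 ≥ 8 − x)

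- p = 0.40: 0.1582 + 0.6472 = 0.8054 (protocol 9.5 states 80.5%).
- p = 0.14: 0.0004 + 0.0129 = 0.0133 (protocol 9.5 states 1.3%).
- Futility at p = 0.40: 0.6^12 + 12(0.4)(0.6^11) = 0.0022 + 0.0174 = 1.96%.
- Futility at p = 0.14: 0.86^12 + 12(0.14)(0.86^11) = 0.1637 + 0.3197 = 48.3%.
- Lan-DeMets O'Brien-Fleming spend at half the information: 0.00153 (stated 0.15%).

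The stated design reproduces. These figures hold exactly when the sets are the first 12 and 24 by consent.

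**Step 2: how fast each outcome is decided.** Protocol 1.3 schedules scans at Cycles 3, 5 and 7 of 28 days, so at weeks 8, 16 and 24. Responses need confirmation at least 4 weeks later (protocol 8.1), so a week-8 response is confirmed on the scheduled scans at week 16.

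- Progression at week 8 is decided 16 weeks before stable disease: 112 / 30.4375 = 3.7 months. At an assumed 1 to 2 participants per month, about 3.7 to 7.4 later participants are dosed in that interval, and any of them who progresses at the first scan can overtake.
- Response confirmed at week 16 is decided 8 weeks before stable disease: 56 / 30.4375 = 1.8 months, or about 1.8 to 3.7 later participants.

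**Step 3: simulation of the rule.** Assumptions that are not in the documents: Poisson accrual of 1 to 2 per month, 24 or 30 evaluable participants enrolled, and decision-time mixes ranging from fast progression with slow response to fast response with little early progression. Responses are confirmed at week 16 or 24, progression occurs at week 8 or 16, and all others are decided at week 24. The consent-to-dose gap is 0 to 28 days, from the protocol's screening window. True ORR is 40% except in the last row.

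| Quantity | First 12 / 24 by consent | Early-decided count toward trigger | 24 weeks elapsed since first dose |
|---|---|---|---|
| Mean interim ORR | 40% | 33–44% | 39.3–40.8% |
| Interim futility stop | 2.0% | 1.2–6.8% | 1.6–2.3% |
| Power, 24 evaluable | 80.5% | 79–81% | 79–82% |
| Power, 30 evaluable | 80.5% | 70–85% | 79–82% |
| Type I error (ORR 14%) | 1.3% | 0.9–2.1% | 1.2–1.6% |

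The last column holds across 24 and 30 enrolled. Its small remainder comes from the consent-to-dose gap.

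**Step 4: sensitivity when early-decided participants count.**

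- A middle mix moves little even up to 4 per month: interim ORR 36.5–39.0%, futility 2.4–3.4%, power about 80% with 24 enrolled and 79% with 30.
- Fast progression at 4 per month gives interim ORR 25.6%, futility 16.6%, and power 73.2% with 24 enrolled or 60.4% with 30.
- Fast response at 4 per month gives interim ORR 49.0%, futility 0.4%, and with 30 enrolled power 91% and type I error 3.2%. Among the cases run on scheduled scans, only this one exceeds 2.5%.

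**The case against.** The strongest reply is that every trigger sentence names 24 weeks. If that is time since first dose, nearly everyone who consented earlier has been decided when the analysis runs, and consent order then picks almost exactly the right set. This stands: under that reading the shift is negligible. But the documents do not settle on it. SAP 3.1 explains evaluation for 24 weeks as having the Cycle 7 assessment, which is not elapsed time, and it admits early-decided participants to the analysed set.

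The second reply is that planned enrolment is about 24, and the clauses for 25 or more are a contingency. This also stands: with exactly 24 evaluable participants there is nothing to select at the final analysis, final ORR is unaffected, and power moves only through the interim.

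Third, all response-evaluable data are analysed as supplemental, and SAP Amendment 1 records that interim results are not meant for the New Drug Application. That keeps displaced participants visible, but it does not change a stopping decision based solely on the 12.

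Two stronger inferences are tempting and not supported:

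- A reader might conclude that the stated type I error and power no longer apply. They hold closely under the elapsed-time reading. With exactly 24 evaluable participants at 1 to 2 per month they also hold closely even if early deciders count.
- A reader might take the trigger to mean that early progressors never count, so that many more than 24 would have to be treated. The same sections expressly include early-determined participants among the analysed 12 and 24, and no document gives the early-loss rate needed to size such an effect. That reading also cannot be combined with the shifts in the table, which assume the opposite.

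**Conclusion.** The point holds in conditional form. The selection rule as written allows membership to depend on how quickly an outcome is known, and the trigger wording does not exclude the version in which this matters.

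If early-decided participants count, the main exposure is the interim futility decision: at 1 to 2 per month its false-stop risk at ORR 40% lies between about 1% and 7% instead of 2.0%. The direction is set by whether progression or response is decided faster. A material effect on final ORR and power also requires more than 24 evaluable participants, or accrual well above 2 per month acting through the interim.

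Accrual, decision-time mix and over-enrolment are assumptions, so the figures are a range and not a forecast. Because the ambiguity bears on a stopping rule and is cheap to remove, it should be corrected before the interim data cutoff is set.

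**What to change.** - In SAP 3.1, define the interim and final sets as the first 12 and first 24 response-evaluable participants by consent date, whatever their decision status. Keep the existing tie-breaks (first-dose date, then site number).
- Run each analysis once every member of its set has met one of conditions 1 to 5. Because evaluability itself needs a postbaseline assessment (or death from progression before one), say that earlier-consented participants whose evaluability is still open are waited for and not passed over.
- Replace the trigger sentences in protocol 9.5 and SAP 1.2 and 3 with this rule, so that one statement governs both timing and membership.

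This restores the design on which the stated 1.3% and 80.5% were calculated. The cost is wording in two documents and possibly some weeks' wait for participants in stable disease, at most about 24 weeks from the last member's first dose. Sample size, boundaries and supplemental analyses are unchanged.
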